8.2.4 Adverse Event Relationship to Study Medication

Causality should be assessed separately for each study drug (MT-3724, lenalidomide) as detailed in the eCRF. If the investigator feels that the event cannot be firmly attributed to one of the study treatments, then the same assessment should be documented for each of the study treatments. Causal relationship to protocol required procedure(s) should also be considered and reported accordingly in the eCRF.

The following should be considered when assessing causality:

- Temporal associations between the agent and the event
- Effect of de-challenge and/or re-challenge
- Pre-existing risk factors
- A plausible mechanism
- Concurrent illnesses.

The investigator and separately, the Medical Monitor on behalf of the sponsor, will determine the causal relationship / relatedness to the study drug(s) according to the classification in the following table:

Classification of adverse events by causality / relationship to the study drug(s)

Causal Relationship	Definition
Definitely related	Follows a reasonable temporal sequence from drug administration, abates upon discontinuation of the drug (de-challenge), is confirmed by reappearance of the reaction on repeat exposure (re-challenge).
Probably related	Follows a reasonable temporal sequence from drug administration, abates upon discontinuation of the drug, cannot be reasonably explained by the known characteristics of the subject's clinical state.
At least possibly related	Follows a reasonable temporal sequence from drug administration, could have been produced by the subject's clinical state or by other modes of therapy administered to the subject.
Unlikely to be related	Does not follow a reasonable temporal sequence from drug administration, is readily explained by the subject's clinical state or by other modes of therapy administered to the subject.
Unrelated	The AE is definitely produced by the subject's clinical state or by other modes of therapy administered to the subject.

For all purposes of subject management, DLT assignment and treatment modification, the causality assessment of “at least probably”, “possibly” or “definitely” will be treated as “related”, while the causality assessment of “unlikely” and not related” will be treated as “unrelated”.

8.2.5 Serious Adverse Events

A serious adverse event (SAE) is any AE that meets one or more of the following criteria:

- The event is fatal or life-threatening.
- The event is permanently disabling (incapacitating or interfering with the ability to resume usual life patterns).
- The event results in unplanned in-subject hospitalization or prolongation of an existing hospitalization.
- Is or results in a congenital abnormality or birth defect.
- Important medical events that may not result in death, be life-threatening, or require hospitalization may be considered serious when, based upon appropriate medical judgment, they may jeopardize the patient or subject or may require medical or surgical intervention to prevent one of the outcomes listed in this definition. Examples of such medical events include allergic bronchospasm requiring intensive treatment in an

emergency room or at home, blood dyscrasias or convulsions that do not result in inpatient hospitalization, or the development of drug dependency or drug abuse.

An AE does not need to be severe in order to be classified as an SAE. For example, an overnight hospitalization for a diagnostic procedure must be reported as an SAE even though the occurrence is not medically serious. In this protocol, the term "severe" is used to describe the intensity (severity) of a specific event according to the CTCAE v.5.0. However, the nominally severe adverse event may be of relatively minor medical significance (such as short-term severe headache or nausea). This is not the same as "serious," which is based on patient/event outcome or action criteria. Seriousness (not severity) serves as a guide for defining regulatory reporting obligations.

8.2.6 Adverse Event Summaries

All AEs (serious and non serious) occurring after completion of the informed consent process and before the end of study, regardless of relationship to study drug, will be included and classified by system organ class (SOC) and preferred term (PT) using the Medical Dictionary for Regulatory Activities (MedDRA).

For treatment-emergent AEs (TEAEs), the following will be summarized and presented for the safety analysis set:

- i. An overall summary of TEAEs, which includes:
 - a. the number and percentage of subjects experiencing a TEAE
 - b. the number and percentage of subjects experiencing a TEAE by relationship to study medication (for each study medication)
 - c. the number and percentage of subjects experiencing a TEAE by greatest grade
 - d. the number and percentage of subjects experiencing a TEAE leading to study dose interruption
 - e. the number and percentage of subjects experiencing a TEAE leading to dose delay
 - f. the number and percentage of subjects experiencing a TEAE leading to dose reduction
 - g. the number and percentage of subjects experiencing a TEAE leading to study withdrawal
 - h. the number and percentage of subjects experiencing a TEAE of special interest (IRR, CRS, and CLS)
 - i. the number and percentage of subjects experiencing a treatment emergent SAE (TESAE)
- ii. the number and percentage of subjects experiencing a TEAE by SOC, PT
- iii. the number and percentage of subjects experiencing a TEAE by SOC, PT and relationship to study medication (for each study medication)
- iv. the number and percentage of subjects experiencing a TEAE by SOC, PT and greatest grade

- v. the number and percentage of subjects experiencing a TEAE leading to dose interruption by SOC and PT
- vi. the number and percentage of subjects experiencing a TEAE leading to dose delay by SOC and PT
- vii. the number and percentage of subjects experiencing a TEAE leading to dose reduction by SOC and PT
- viii. the number and percentage of subjects experiencing a TEAE leading to study withdrawal by SOC and PT
- ix. the number and percentage of subjects experiencing a TEAE of special interest by SOC and PT
- x. the number and percentage of subjects experiencing a TESAE leading to dose interruption by SOC and PT
- xi. the number and percentage of subjects experiencing a TESAE leading to dose delay by SOC and PT
- xii. the number and percentage of subjects experiencing a TESAE leading to dose reduction by SOC and PT
- xiii. the number and percentage of subjects experiencing a TESAE leading to study withdrawal by SOC and PT
- xiv. the number and percentage of subjects experiencing a TESAE of special interest by SOC and PT

In the overall summary of TEAEs table (i), besides tabulating the number and percentage of subjects, the total number of TEAE episodes will also be provided. If a subject has repeated episodes of a particular TEAE, all episodes will be counted in the summary table.

In the remaining summary tables, the incidence of TEAEs will be calculated by dividing the number of subjects who have experienced the event by the total number of subjects in the safety analysis set. Thus, the incidence of TEAEs is shown in terms of the total number of subjects and not in terms of the total number of episodes. If a subject has repeated episodes of a particular TEAE, only the most severe episode, or the episode with the strongest causal relationship to study drug, will be counted in the summary tables.

A subject with more than one type of TEAE in a particular SOC will be counted only once in the total of subjects experiencing TEAEs in that particular SOC. Since a subject could have more than one type of TEAE within a particular SOC, the sum of subjects experiencing different TEAEs within the SOC could appear larger than the total number of subjects experiencing TEAEs in that SOC. Similarly, a subject who has experienced a TEAE in more than one SOC will be counted only once in the total number of subjects experiencing AEs in all SOCs.

All occurrences of all AEs will be listed for each subject, grouped by cohort. The listing will contain the following information: treatment group, verbatim term, SOC, PT, severity, relationship to study medication, date and day of onset, date and day of resolution, treatment given to treat the adverse event, the outcome, whether the event was an SAE, whether it led to withdrawal and whether it is a TEAE. Listings will be sorted by subject identification number, onset date, SOC, and PT. If the onset date is completely missing, then these events will be presented first. If the

onset date is missing a month or a day, then these events will be presented before any complete dates.

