3.4 End of Treatment Visit and Short-Term Follow-Up phone call

The EoT Visit will be performed at the end of the treatment period for each subject in Part 1 and Part 2. The EoT Visit should occur at the time of discontinuation, as soon as possible after the last dose of MT-3724 or LEN (within 14 days of last dose) for all subjects, except those who withdrew consent and objected to further data collection, or were lost to follow up.

The EoT Visit should be performed during the clinic visit. The EoT Visit may be performed by telephone call, but only if a subject cannot attend a clinic visit or has started a new anticancer treatment. In such instances, missed assessments (e.g., laboratory assessments, PE), are not considered deviations.

The STFU phone call will take place at least 30 days (+7 days) after the last dose of MT-3724 or LEN (except for subjects who withdrew consent and objected to further data collection, or were lost to follow up).

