5.8 Treatment duration

In Part 1 and Part 2, the treatment with MT-3724 and/or LEN in this study may be continued until death, progressive disease, AE requiring discontinuation or withdrawal of consent, any other reason for study discontinuation, or until study discontinuation. Thereafter, the subject will undergo the EoT Visit and STFU phone call.

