6.2.6 Vital signs

Vital signs include blood pressure (BP), heart rate (HR), respiratory rate (RR), and body temperature (°F or °C). BP and HR will be measured after 5-10 minutes of quiet rest in a sitting or semi-recumbent position using an automatic (preferred) or manual BP measuring device.

Vital signs will be assessed at the following time points:

- At screening
- Before the start of each MT-3724 infusion in each cycle;
- At 0.5h, 1h and 2h (±10 min allowed at each time point) after the start of each MT-3724 infusion in each cycle
- At 3h and 4h (±10 min allowed at each time point) after the start of MT-3724 infusion on C1D1
- At the EoT Visit

Unscheduled VS measurements may be performed at investigator's discretion in each cycle.

Any clinically-significant abnormality in VS should be investigated by repeat assessments (number and timing at investigator's discretion). The confirmed clinically significant abnormalities should be reported as AE in the eCRF.

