6.3 Adverse events

The term adverse event is defined as any untoward medical occurrence in a subject or clinical investigation in a subject administered a pharmaceutical product(s) and which does not necessarily have to have a causal relationship with this experimental treatment(s).

An AE is any symptom, physical sign, syndrome, or disease that either emerges during the study or, if present at screening, worsens during the study, regardless of the suspected cause of the event. All AEs that occur in enrolled subjects during the AE reporting period specified in the protocol must be recorded, regardless of the relationship of the AE to study drug.

All medical and psychiatric conditions (except those related to the indication under study) present at screening will be documented on the Medical History CRF page. Clinically significant worsening in these conditions and new symptoms, physical signs, syndromes, or diseases should be noted on the AE eCRF page during the rest of the study. Laboratory, VS, and ECG abnormalities should also be recorded as AEs when considered clinically significant and representing a change from pre-treatment baseline.

Surgical procedures themselves are not AEs; they are therapeutic measures for conditions that require surgery. The condition for which the surgery is required may be an AE. Planned surgical measures for preexisting, non-worsening conditions permitted by the clinical study protocol and the condition(s) leading to these measures are not AEs. Except when the event would qualify as serious (e.g. leading to hospitalization).

Adverse events will be assessed by verbal probes and subject's spontaneous reports at screening and during every post-baseline clinic visit and telephone contact from the start of treatment until the STFU Visit. Information will be collected by trained, qualified study staff and the information will be recorded in the appropriate eCRFs. At a minimum, all relevant information regarding the AE and concomitant medication use will be captured.

All AE reports (solicited or volunteered) will be reviewed and followed by the responsible investigator and medical monitor qualified delegate for completeness, relatedness and accuracy of severity grading in order to ensure appropriate reporting practice. Cumulative AE data will be reviewed periodically by the medical monitor as well as *ad hoc* review of serious and/or severe AEs as they are reported.

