6.3.1 AE reporting period

The AE reporting period will begin on the day of the first dose of study drug until the STFU call, or until the start of new cancer therapy (unless the investigator believes the AE is related to MT-3724), whichever occurs first.

Grade ≥ 2 AEs related to MT-3724 and/or LEN that were ongoing at the STFU Visit should be followed by the investigator until all events have resolved to Grade ≤ 1 .

Those AEs that occur after the first dose on C1D1 will be considered treatment-emergent.

All AEs that occur in enrolled subjects during the AE reporting period specified in the protocol must be recorded, regardless of the relationship of the AE to MT-3724 or LEN. Any serious known untoward event that occurs beyond the AE reporting period that the investigator assesses as at least possibly related to MT-3724 should also be reported to the sponsor.

For AEs of CLS, CRS/SIRS, and IRRs, individual symptoms and grade should be reported on the appropriate CRF.

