7.8 Safety analyses

The primary analysis of safety will be a comprehensive evaluation of AEs and/or toxicity, presented by dose, regimen and tumor type cohort and overall, based on:

- The type, incidence, severity, timing, seriousness, and relatedness of adverse events.
- Incidence of DLT and TEAEs that led to treatment modification
- Recording of IRR, CRS and CLS
- Results of monitoring vital signs (BP, HR, RR and body temperature)
- Results of clinical chemistry, hematology, thyroid function, coagulation, and urine analysis tests
- ECG results
- Changes in physical examination
- Results of immunogenicity assessments ADA and NAb
- Need for concomitant medications

All safety analyses will be descriptively summarized based on the safety population.

AEs/SAEs will be coded and tabulated using the current version of MedDRA. Each AE will be classified by system organ class and preferred term. All AEs along with the coded terms will be listed.

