6. Other changes to inclusion/exclusion criteria have been made to ensure consistency across the MT-3724 program of studies and to modify criteria which were unnecessarily stringent. These latter changes include allowing subjects with seropositive human immunodeficiency virus (HIV)/hepatitis B virus (HBV)/hepatitis C virus (HCV) the option to enroll in this study provided they have non-detectable viral loads (HIV/HBV/HCV), a minimum number of CD4+ cells (for subjects with HIV) and receive appropriate prophylactic treatments. The current safety data do not indicate a heightened risk for study subjects to have new or reactivated infectious diseases. Also, a reduced washout period (consistent with the relevant half-life for subjects whose last treatment include small molecules, as opposed to monoclonal antibodies) is implemented.

7. The protocol was modified to allow subjects continued treatment with MT-3724, rather than the prior limitation of therapy to a maximum of 12 cycles, contingent upon demonstration of continued clinical benefit and tolerability of study treatment. Given the current safety profile which includes subjects' exposure for up to 9 cycles, it is reasonable to allow subjects continued treatment with MT-3724 as long as there is a favorable risk-benefit ratio in the opinion of the investigator.
8. The screening period has been increased from 28 days to 35 days to allow for central laboratory processing of screening samples
9. The safety event collection period starting point has been updated from "signing of the informed consent" to "Cycle 1 Day 1". This was implemented to avoid collecting unrelated pre-treatment AEs; and to avoid confounding understanding of MT-3724 safety profile with toxicities from other cancer therapies. An AE/SAE during the screening period will only be collected if it is deemed related to a protocol screening procedure.
10. Respiratory rate and temperature assessments have been added to vital signs and quality of life analysis language has been added as these were inadvertently omitted from previous versions of the protocol.
11. Vast majority of changes made were to provide clarifications to existing language.

High-level summary of changes made:

Section	Change	Rationale

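### TEAE percentages by cohort need a fixed-window table and exposure-adjusted rates beside them, because treatment is uncapped and AE collection follows time on drug

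*SAP*

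**What the plan says.** - **Incidence.** SAP 8.2.6 gives a crude proportion of the safety analysis set: "incidence of TEAEs will be calculated by dividing the number of subjects who have experienced the event by the total number of subjects". There is no person-time term and no time window. Read literally, the denominator is the whole safety set, not the cohort's own N.
- **Presentation.** Protocol 7.8 wants the primary safety evaluation "presented by dose, regimen and tumor type cohort and overall", and 7.8.1 repeats the breakdown by treatment group or cohort. SAP 5 reports escalation and expansion cohorts separately and also combined at the recommended dose.
- **Treatment time.** Under Protocol 5.8, "the treatment with MT-3724 and/or LEN in this study may be continued until death, progressive disease, AE requiring discontinuation or withdrawal of consent", with no maximum number of cycles. Appendix 9 explains that continued treatment is now allowed "rather than the prior limitation of therapy to a maximum of 12 cycles".
- **AE window.** Protocol 6.3.1: "The AE reporting period will begin on the day of the first dose of study drug until the STFU call", or until new cancer therapy if that comes first. Protocol 3.4 fixes the tail: "The STFU phone call will take place at least 30 days (+7 days) after the last dose of MT-3724 or LEN".
- **Exposure.** SAP 8.1 summarises number of doses, expected and actual dose, and infusion outcome. It does not summarise time on treatment.
- **Timing.** Protocol 7.8 names the timing of AEs as part of the primary safety analysis. In the SAP, onset and resolution days appear only in a listing.

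**The concern.** Safety and tolerability is the primary objective, and the by-cohort TEAE tables are its main display. A subject's chance of being counted depends on the event rate and on how long the subject is observed, and here observation lasts as long as treatment plus about a month. A cohort that stays on drug longer, because it responds better or tolerates the dose better, collects more ever/never events at an unchanged rate. A cohort that stops early has less time in which to show them. The start of new cancer therapy closes the window earlier still, so observation time is tied to outcome.

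Time on drug may well differ between the two parts. Part 1 admits all B-cell NHL subtypes and Part 2 only DLBCL (Protocol 4.1, criterion 4), and the two are to be shown side by side and pooled. A reader of the planned tables could not tell a difference in toxicity from a difference in follow-up, because treatment duration is not tabulated either.

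**Working it through.** **Stated figures.** The documents give no AE rate, expected treatment duration, power or alpha. The only total is 24 + 40 = 64 subjects, with no formula behind it. There is no planned figure to reproduce, so every rate and duration below is an assumption.

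**1. Effect of duration alone.** With a constant rate λ of first events per subject-month, crude incidence after T months of observation is 1 − exp(−λT).

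| λ per month | T = 2 | T = 6 | T = 9 | Gap, 2 vs 6 |
|---|---|---|---|---|
| 0.10 | 1 − exp(−0.2) = 18.1% | 1 − exp(−0.6) = 45.1% | 1 − exp(−0.9) = 59.3% | 27.0 points |
| 0.20 | 1 − exp(−0.4) = 33.0% | 1 − exp(−1.2) = 69.9% | 1 − exp(−1.8) = 83.5% | 36.9 points |

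Nine cycles appears in Appendix 9 as the longest exposure so far. It is not a typical cohort duration.

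**2. Adding the 30-day tail.** With rate L per 28-day cycle and c cycles of treatment, incidence is 1 − exp(−L(28c + 30)/28). The exponent multiplier is 86/28 = 3.07 for c = 2 and 198/28 = 7.07 for c = 6.

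| L per cycle | 2 cycles | 6 cycles | Gap |
|---|---|---|---|
| 0.05 | 14.2% | 29.8% | 15.6 points |
| 0.10 | 26.4% | 50.7% | 24.3 points |
| 0.20 | 45.9% | 75.7% | 29.8 points |

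**3. Time on treatment varying between subjects.** Take it as exponential with median m months, so the stopping rate per cycle is μ = ln 2/(m × 30.44/28), and incidence is 1 − [μ/(L + μ)] exp(−L × 30/28). As an anchor, Protocol 1.3.1 cites a median PFS of 3.7 months for lenalidomide plus rituximab. With L = 0.10, m = 2, 3.7 and 7.4 months give 31.6%, 43.2% and 58.4%.

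**4. Limiting case.** If all the risk falls in cycle 1, later treatment time adds nothing and the gap is zero.

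**5. Whether the proposed additions remove the effect.** At L = 0.10, expected time to first event or end of window is (1 − exp(−LT))/L per subject. Events over person-time is then L = 0.10 per cycle for both the 2-cycle and the 6-cycle cohort. A cycle 1 window gives 1 − exp(−0.10) = 9.5% in both.

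**6. Precision.** Exact 95% limits in a cohort of 6 are 4% to 78% for 2/6 and 12% to 88% for 3/6.

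**7. Contact frequency by schedule.** Protocol 6.2.6 sets readings before and at three times "after the start of each MT-3724 infusion in each cycle", plus two extra on C1D1. Under Protocol 5.1.3, Cohorts 1–3 have 6 infusions in each of cycles 1 and 2, later cohorts have 4, and all have 4 from cycle 3. Vital-sign sets are therefore 6 × 4 + 2 = 26 versus 4 × 4 + 2 = 18 in cycle 1, 24 versus 16 in cycle 2, and 16 versus 16 afterwards. Hematology, chemistry and urinalysis fall on D1, D8 and D15 for every cohort (Protocol 6.4.1), so 3 versus 3 per cycle.

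**The case against.** Crude incidence is the usual display in a descriptive early-phase study, and SAP 8 plans no testing between dose levels. Doses are not chosen from these tables. Escalation and the MTD rest on DLTs (Protocol 3.6 and 3.6.3), whose default window is cycle 1 (3.6.2) and which have their own table by dose level (SAP 8.2.7). The constant rate in the illustration is an assumption; Appendix 9 itself describes innate immune responses as an early cycle 1 phenomenon, and for those the duration effect vanishes. In cohorts of 3 to 6, sampling error exceeds the shift. All of this stands. It limits the consequence but does not supply the missing denominator for events that accrue later.

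A reader might also infer from the visit counts that cohorts dosed more often look more toxic by construction. The documents do not support that:
- More infusions can cause more toxicity, which the table should show.
- The schedules differ only in cycles 1 and 2, and safety laboratories are on common days.
- Only confirmed, clinically significant vital-sign abnormalities become AEs.
- AEs are asked about "during every post-baseline clinic visit and telephone contact from the start of treatment until the STFU Visit", so an event between visits can still be picked up at the next contact.

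Nor is a separate vital-sign comparison on matched nominal days needed. SAP 8.5 already summarises vital signs at each visit, and SAP 5.3 assigns data by CRF visit. Only the shift to the maximum post-baseline value is not aligned in time.

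**Conclusion.** The gap is real but modest. The by-cohort TEAE tables have no common time basis, and nothing planned lets a reader correct for that. For accruing events, the distortion between 2 and 6 months is about 27 to 37 points at constant rates of 0.10 to 0.20 per month, or about 16 to 30 points between 2 and 6 cycles at 0.05 to 0.20 per cycle with the 30-day tail included. These sizes rest on assumed constant rates and assumed durations; for events confined to cycle 1 the distortion is nil.

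A reader might go on to infer that the trial could select the wrong dose. That does not follow, because the cycle 1 DLT rule drives the decision, although the sponsor may add later events as DLTs. The practical exposure is in reporting: the expansion cohort of about 40 beside, or pooled with, small escalation cohorts. Even there the escalation side stays noisy. This is a cheap improvement to the SAP, not a flaw in the design.

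**What to change.** Keep the crude tables, and state that percentages by cohort use the cohort's own N. For overall TEAEs, Grade ≥3, related TEAEs, TESAEs, and IRR/CRS/CLS, add:

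1. **A cycle 1 TEAE incidence table by cohort (dose and schedule)**, named as the basis for comparing cohorts. Define when cycle 1 ends, so that a delayed cycle 2 does not lengthen the window.
2. **Exposure-adjusted first-event rates** (subjects with the event per subject-month at risk) with exact Poisson 95% CIs, split cycles 1–2 versus ≥3. Time at risk runs from first dose to the earliest of first event, STFU call, start of new cancer therapy, death or last contact. Running it to STFU for everyone would overcount, because reporting normally stops at new therapy. Drug-related events reported after that point under the exception in Protocol 6.3.1 should be listed and kept out of the rate.
3. **Treatment duration by cohort in SAP 8.1**, for each drug and for either drug.

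Before these are derived, SAP 3.2.1 and Protocol 5.1.3 must be reconciled. The SAP describes six infusions in each of cycles 1 and 2 for all subjects, while the protocol separates Cohorts 1–3 from later cohorts.

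Cost: a few tables from data already collected, and no protocol amendment for the added tables. Downside: sparse cells and wide intervals in cohorts of 3 to 6, especially for the split rates.
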